## 9.0. AIMS

[figure not shown]
The overall goal of our Protocol Leadership Group (PLG) is to produce first-ever evidence on the effectiveness of a proven pragmatic lifestyle intervention targeted at modest, clinically meaningful weight loss and increased physical activity in overweight or obese patients with spirometry-confirmed COPD. In the 12-month simple, pragmatic clinical trial (PCT), we efficiently focus on the intervention effects primarily on exercise tolerance; and secondarily on weight loss, dyspnea, generic and symptom-specific quality of life (QoL), and cardiovascular risk factors (CVRFs).

We will implement the E-LITE self-directed lifestyle intervention in a multicenter, patient-level randomized PCT of approximately 680 overweight and obese patients with COPD. Our specific aims are to test whether, compared with usual care (UC) controls, intervention participants have better outcomes through 12 months of follow-up, including:

1. **Primary measures:** Exercise tolerance measured with the 6-Minute Walk Test (6MWT) distance at 12 months (primary endpoint).
2. **Secondary measures:** Greater weight loss, less dyspnea measured with the modified Borg scale, improvements in generic HRQoL by the SF-12v2, COPD symptom QoL by the SGRQ-C, and major CVRFs (central obesity by waist circumference, Framingham Risk Score, blood pressure, and BMI).

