#### 14.6. Sensitivity Analyses

We will summarize and visualize our outcomes based on missingness patterns across time. If this investigation produces evidences of missingness not at random, a multiple imputation using chained equations (MICE) approach will be implemented as a sensitivity analysis for each primary analysis model, with Rubin's rules employed to pool inference across analyses of completed datasets.

We will also investigate whether the distribution of follow-up measurement time differs across treatment arm. If a difference is evidenced, each primary analysis model and MICE sensitivity analysis model, if using, will be re-fit with a continuous covariate that counts the number of days from 12-months post-randomization date to actual follow-up measurement date.

Additional covariates (e.g., age, sex) will be included to elucidate the primary intention-to-treat findings regarding treatment arm difference in our outcomes at 12-month follow-up. Further sensitivity analyses will be conducted using Generalized Estimating Equations (GEEs) if the distributional assumption of normality is not met within the LMM framework. GEEs do not rely on this distributional assumption and will allow for an evaluation of the intervention in this scenario.

#### 14.7. Secondary Analysis for Aim 1

Dichotomized secondary outcomes for 6MWT distance, weight, and post-walk modified Borg dyspnea scale will be generated based on whether the respective, continuously measured primary outcome meets or exceeds the minimal important difference, as described below:

- 6MWT distance: 30m
  - Dichotomous outcome is equal to 1 if (follow-up 6MWT distance - baseline 6MWT distance)  $\geq$  30m, and it is equal to 0 otherwise.
- Weight: (Multiple)
  - Dichotomous outcome is equal to 1 if (follow-up weight – baseline weight)/(baseline weight)\*100%  $\geq$  5%, and it is equal to 0 otherwise.
  - Dichotomous outcome is equal to 1 if (follow-up weight – baseline weight)/(baseline weight)\*100%  $\geq$  3%, and it is equal to 0 otherwise.
- Post-walk modified Borg dyspnea scale (i.e., shortness of breath): 1 unit
  - Dichotomous outcome is equal to 1 if (baseline shortness of breath - follow-up shortness of breath)  $\geq$  1 unit, and it is equal to 0 otherwise.

Mixed-effects logistic regression models of the following form will be fit to these secondary outcomes and used to estimate a treatment arm standardized risk difference:

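### Both weight responder outcomes have the subtraction reversed, so code 1 marks a gain of at least 5% or 3% of body weight instead of a loss

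*Combined protocol and SAP*

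**What the plan says.** Section 14.7 creates 0/1 versions of three outcomes. The stated purpose is to record whether the "continuously measured primary outcome meets or exceeds the minimal important difference, as described below". The rules are:

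- **6MWT distance:** "Dichotomous outcome is equal to 1 if (follow-up 6MWT distance - baseline 6MWT distance") is at least 30 m.
- **Weight, two rules:** "Dichotomous outcome is equal to 1 if (follow-up weight – baseline weight)/(baseline weight)\*100", expressed as a percentage, is at least "5%, and it is equal to 0 otherwise"; the second rule has the same numerator and ends "3%, and it is equal to 0 otherwise".
- **Post-walk Borg dyspnea:** "Dichotomous outcome is equal to 1 if (baseline shortness of breath - follow-up shortness of breath") is at least 1 unit.

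Neither weight rule contains a minus sign or an absolute value. These variables feed mixed-effects logistic models that estimate a standardized risk difference between arms.

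Elsewhere the plan treats loss as the desired direction for weight. The secondary aims in Section 9.0 begin "Greater weight loss, less dyspnea measured with the modified Borg scale". Section 10.6.2 sets the intervention goal at a 5-10% loss from baseline. Section 6.0 describes a 3-5% loss as modest and beneficial, which matches the two cut-points.

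**The concern.** Weight and Borg dyspnea are both outcomes where lower is better. For Borg the plan subtracts follow-up from baseline, so that improvement is positive. For weight it keeps the order used for walk distance, where higher is better. Only the two weight rules point away from benefit.

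If the rules are programmed literally, an intervention that works shows a negative responder difference, and one that causes weight gain shows a positive one. The error could also spread. Section 14.7 says waist circumference, BMI, blood pressure and the Framingham score will be analysed in a similar way, and gives no direction or cut-point for any of them.

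**Working it through.** The plan gives no numerical result for these outcomes, so there is no figure to reproduce. The check has two parts.

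**1. The rule on test weights.** Let B be baseline weight, F follow-up weight and t the threshold (5 or 3, Section 14.7).

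- As written: 1 if (F - B)/B × 100 ≥ t
- Intended: 1 if (B - F)/B × 100 ≥ t

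With B = 100:

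| F | Change | Written, 5% | Written, 3% | Intended, 5% | Intended, 3% |
|---|---|---|---|---|---|
| 90 | -10% | 0 | 0 | 1 | 1 |
| 95 | -5% | 0 | 0 | 1 | 1 |
| 97 | -3% | 0 | 0 | 0 | 1 |
| 100 | 0% | 0 | 0 | 0 | 0 |
| 103 | +3% | 0 | 1 | 0 | 0 |
| 105 | +5% | 1 | 1 | 0 | 0 |
| 110 | +10% | 1 | 1 | 0 | 0 |

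The row F = 100 shows why relabelling cannot rescue the variable. Stable weight is 0 under both rules. If the written codes were swapped, everyone with stable weight would become a responder.

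**2. Effect on the risk difference.** The documents give no mean or SD of percent weight change for this population, so these inputs are assumptions. Take percent change as normal with arm mean m and standard deviation s, and let Φ be the standard normal distribution function.

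- Proportion coded 1 as written: 1 - Φ((t - m)/s)
- Proportion coded 1 as intended: Φ((-t - m)/s)

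Worked case: intervention mean -3%, control mean 0%, SD 5%, t = 5.

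- Written, intervention: 1 - Φ((5 + 3)/5) = 1 - Φ(1.6) = 5.5%
- Written, control: 1 - Φ(5/5) = 1 - Φ(1.0) = 15.9%
- Written risk difference: 5.5 - 15.9 = -10.4 points
- Intended, intervention: Φ((-5 + 3)/5) = Φ(-0.4) = 34.5%
- Intended, control: Φ(-1.0) = 15.9%
- Intended risk difference: 34.5 - 15.9 = +18.6 points

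Four further scenarios, as risk differences in percentage points (intervention minus control):

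| Mean intervention / control, SD | 5% written | 5% intended | 3% written | 3% intended |
|---|---|---|---|---|
| -2 / 0, 5 | -7.8 | +11.6 | -11.6 | +14.6 |
| -3 / -0.5, 6 | -8.8 | +14.3 | -12.1 | +16.1 |
| -4 / -1, 6 | -9.2 | +18.1 | -13.1 | +19.7 |
| -5 / -1, 7 | -11.9 | +21.6 | -15.7 | +22.5 |

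Crossing all the values (intervention -2, -3, -4, -5; control 0, -0.5, -1; SD 5, 6, 7) gives wider ranges:

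- **5% rule:** -16.1 to -3.4 as written, +5.0 to +34.1 intended.
- **3% rule:** -21.9 to -4.6 as written, +5.6 to +38.1 intended.

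The signs are opposite in every combination. The sizes differ as well, so changing the sign of the written result would not recover the intended one.

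**The case against.** The strongest case on the other side is about containment. The error touches only dichotomized versions of a secondary outcome. Section 14.5 also analyses weight as a continuous variable, and that contrast does not use this rule. The primary endpoint and its own 30 m responder rule are sound. Section 14.1 describes the secondary analyses as complementary and unadjusted for multiplicity. The intended direction is clear from the rest of the protocol, so an analyst would probably notice, and a wrong-signed responder result would clash visibly with the continuous one.

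All of this is true, and it limits the damage: the trial's main conclusion is not at risk. It does not make the rule correct. The same numerator appears in both rules, in a section whose analysis plan was updated for version 5.10, and no other text corrects it. Following it gives the wrong endpoint. Correcting it silently is an undocumented departure from a prespecified definition.

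Two smaller points also stand. Code 0 under the written rule covers stable weight and small gains as well as losses, and the plan does not itself use the terms success and failure. The illustrative sizes depend on assumed distributions. Neither point changes the finding about direction.

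**Conclusion.** The rule is wrong as written. Both weight responder outcomes identify participants who gained weight, although the aim, the intervention goal and the neighbouring rules all require loss. This follows from the algebra alone and needs no distributional assumption.

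The size of the effect on the risk difference does rest on assumption: normal percent change with the means and SDs listed above. Only the opposite signs should be relied on, not any single value. The error must be corrected before analysis. Its reach is limited to the two dichotomized weight outcomes, plus any similarly derived outcome that copies the same template.

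**What to change.** In Section 14.7, define the two weight outcomes as 1 if (baseline weight - follow-up weight)/(baseline weight) × 100% is at least 5%, and at least 3% respectively. An equivalent form keeps the present numerator and uses the conditions ≤ -5% and ≤ -3%.

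Limit this correction to the sign. How a missing follow-up weight is coded is a separate question that applies equally to the 6MWT and Borg rules. For the outcomes that are to be handled similarly, state the direction of benefit and any cut-point, so that the reversal is not repeated.

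The cost is one line per rule, entered as a dated correction before the analysis is run. It has no effect on participants, data collection or sample size.

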### 10.3. **Randomization**

All of the baseline assessment measures listed in Tables 5 and 6 must be completed prior to randomization. A site coordinator will randomize the participant using the REDCap randomization function. The unit of randomization will be the participant, performed at a ratio of 1:1. We will stratify each site on smoking status (current smoker vs. non-smoker). In order to maintain blinding of the outcome assessors to the randomization assignment, sites may choose to:

- Have one coordinator conduct the baseline assessment, conduct randomization, and orient those in the intervention arm to the intervention, then have a different trained coordinator conduct 12-month outcome assessments; or
- After baseline assessment, hand-off the participant to a different coordinator who only will conduct randomization and orient participants to the intervention, and who will not conduct outcome assessments.

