## 14.0. ANALYSIS

### 14.1. Sample size

The primary endpoint is 6MWT distance at 12 months, a continuous scale outcome. An overall sample size of 680, with 340 in each treatment group, will allow detection of a standardized mean difference (Cohen's  $d$ ) of 0.28 between the intervention and UC groups with a power of 90%, two-sided  $\alpha = 0.05$ , and assuming at least 80% retention at 12 months. The decision to use a Cohen's  $d$  of 0.28 is based on based on 30m as the MID for 6MWT distance. In the CONCERT study, the Cohen's  $d$  effect size was approximately 0.39 for 6MWT distance between the overweight and obese groups. A two-sample t-test is used to estimate power (**Table 11**). No multiplicity adjustment will be made for secondary analyses, which are intended to complement the primary findings and to inform future research. They will be interpreted within that context, considering the totality of evidence available.

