### 14.2. Overview of analysis plan

This is a patient-randomized trial with patients nested within site and repeated measures within patient. This type of design makes it invalid to use standard approaches to assess a patient-level randomized trial because of the correlation between patients within site and repeated measures within patient. For the primary analysis, we will be evaluating the effect of the intervention at the primary endpoint (12 months through modeling of baseline and 12-month outcomes). It is reasonable to expect that patients within a site are not independent of one another and that repeated measures within patient are not independent from one another. These effects, depending on the correlations within and across sites and patients, may lead to decreased variance at the outcome measurement level and increase the probability of a type I error. The primary research hypothesis to be tested is that the intervention will lead to net improvement in 6MWT distance at 12 months. A linear mixed-effects model (LMM) will be necessary to assess the effect of the treatment. The statistical test will be two-sided because it is possible that the control group is superior to the intervention in either outcome measure. In other words, the statistical alternative hypothesis is two-sided, namely, the two study groups will result in significantly different 6MWT distances at 12 months.

Statistical analysis will occur in two phases. First, preliminary analyses will be performed to examine the suitability and feasibility of assumptions required to conduct more complex analysis including distributional assumptions (e.g., variance homogeneity, normality, etc.), collinearity and independence will be carried out. Second, we will conduct hypothesis testing analyses for the specific aims as described below.

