### 14.3. Baseline Analysis and Descriptive Statistics

Equivalence of participants in the intervention and control arms will be assessed on demographic and clinical variables, including outcomes, health status, co-morbidity, and utilization variables. Because this is a randomized controlled trial, no systematic bias is anticipated. However, we will conduct sensitivity analyses that adjust for the covariates that are thought a priori to be related to the primary and secondary outcomes (e.g., age, sex). We will report summary statistics for all baseline covariates and outcomes (means, standard deviations, and quartiles for continuous variables; frequencies and percentages for binary variables) by randomized treatment group.

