### 14.4. Drop Outs and Missing Data

We will make every effort to obtain complete data on each study participant at all data collection points. However, some missing data is inevitable and creates a risk for selection bias that can skew results. We will document and evaluate the extent, pattern, and reasons for missing data. Our primary analysis model will

handle missing data using restricted maximum likelihood (REML) estimation which relies on the assumption that the data is missing at random (MAR). ML has been shown to yield similar results to its alternative multiple imputation (MI). ML is a powerful alternative to MI and valid for our data as we will collect all patient demographics prior to randomization. This means that we expect to have no missing values in our explanatory variables, which is a necessary criterion for REML. For the MAR assumption to hold, it must be believed that the probability the outcome is missing depends only on the information available. In the case of this study, this assumption should be acceptable as the missing outcome variables should be explained by the available variables. However, should the MAR assumption appear to be violated, we will conduct sensitivity analyses that instead assume the data are missing not at random. In this case, it is necessary to account for the missing data mechanism in the model.

#### 14.5. Primary Analysis for Aim 1

The primary analysis will use intention-to-treat and all available data in model fitting. Our continuous primary outcomes and important secondary outcomes – 6MWT distance (primary), weight (secondary), and post-walk modified Borg dyspnea scale (secondary) – will be modeled via mixed-effects linear regression of the following form:

$$y_{ijk} = \beta_0 + \beta_1 k + \beta_2 (\text{Intervention}_i * k) + \beta_3 \text{COVID}_{ik} + \beta_4 \text{BaselineSmoker}_i + \alpha_i + \gamma_j + e_{ijk}$$

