$$y_{ij} = \beta_0 + \beta_1 \text{Intervention}_i + \beta_2 \text{COVID}_i + \beta_3 \text{BaselineSmoker}_i + \gamma_j + e_{ij}$$

Where  $y_{ij}$  stands for the dichotomized outcome for patient  $i$  of site  $j$ .  $\text{Intervention}_i$  is an indicator variable equal to 1 for patients randomized to the intervention arm and is equal to 0 otherwise.  $\text{COVID}_i$  is an indicator equal to 1 for patients whose follow-up outcome was measured on or after March 19, 2020 and is equal to 0 otherwise.  $\text{BaselineSmoker}_i$  is equal to 1 if patient  $i$  reported smoking within one month prior to baseline self-report and is equal to 0 otherwise. The  $\gamma_j$  are random site-level intercepts assumed independently distributed Normal(0,  $\sigma_\gamma^2$ ), and the  $e_{ijk}$  are outcome-level errors assumed independently distributed Normal(0,  $\sigma^2$ ).

Additional secondary outcomes – generic HRQoL, Framingham CVD Risk Score, waist circumference, blood pressure, and BMI – will be analyzed similarly as in the primary and secondary analyses of 6MWT distance, weight, and post-walk modified Borg dyspnea scale.

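### The responder models in section 14.7 leave out the baseline value of the outcome they dichotomise, although the primary model in section 14.5 uses it

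*Combined protocol and SAP*

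**What the plan says.** Section 14.7 builds each responder on whether the "continuously measured primary outcome meets or exceeds the minimal important difference". For 6MWT this is a gain of at least 30 m, for post-walk Borg a fall of at least 1 unit, and for weight a percentage change from baseline. It then states: "Mixed-effects logistic regression models of the following form will be fit to these secondary outcomes". The model for these outcomes has arm, a COVID indicator set to 1 "for patients whose follow-up outcome was measured on or after March 19, 2020", baseline smoking and a random site intercept, and it is used to obtain a standardised risk difference. The baseline value of the outcome is not a term.

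Section 14.5 is built differently. Baseline is the outcome at k = 0, arm enters only through its product with k, and a random patient intercept links the two visits. Section 14.2 describes this as evaluating the effect at "12 months through modeling of baseline and 12-month outcomes", and section 14.5 adds: "The primary analysis will use intention-to-treat and all available data in model fitting".

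The baseline value is always available. Section 10.3 states: "All of the baseline assessment measures listed in Tables 5 and 6 must be completed prior to randomization". Section 14.3 plans "sensitivity analyses that adjust for the covariates that are thought a priori to be related to the primary and secondary outcomes (e.g., age, sex"), and section 14.6 repeats the same two examples for the primary findings. Neither section names the baseline outcome or alters the 14.7 model.

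**The concern.** Subtracting baseline to form a change is not the same as adjusting for baseline. Patients who start high tend to fall back and those who start low tend to gain, so the chance of being a responder depends on where a patient starts. For Borg this follows from the scale itself: it stops at 0, so a patient whose baseline post-walk score is below 1 cannot fall by 1 unit.

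A baseline difference between arms, whether from chance or from loss to follow-up, therefore moves the responder difference with no treatment effect behind it. The 14.5 model corrects for this because the arms share one baseline mean. It also keeps the baseline of patients who are lost. The 14.7 model needs the 12-month value, so it drops those patients and takes no account of their baseline. The two results for the same outcome could drift apart for reasons unrelated to treatment. What is at stake is some precision and the coherence of a secondary result, not the primary test.

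**Working it through.** **Anchor: the plan's own power.** Completers needed per arm at d = 0.28, two-sided alpha 0.05 and 90% power: 2(1.960 + 1.282)²/0.28² = 268.04, so 269. Dividing by 0.8 gives 337 randomised, against 336 and 268 in Table 11 and 340 in section 14.1. With 0.8 × 340 = 272 completers per arm, power is 90.4%, against the stated 90%. The plan's figure reproduces.

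**Inputs**
- SD of 6MWT: 30.2/0.28 = 107.9 m (Table 11; the other rows give 107.8 and 107.9).
- Effect and cut-off: 30 m, from "30m as the MID for 6MWT distance" (section 14.1) and section 14.7.
- 340 per arm with 20% loss (section 14.1).
- Correlation of baseline with 12-month 6MWT: not in the documents. Assumed 0.75, range 0.6 to 0.85.

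**True responder difference (Normal model, no mean change in controls).** SD of change = 107.9 × √(2 − 2 × 0.75) = 76.3 m.
- Controls: P(change ≥ 30) = 1 − Φ(30/76.3) = 34.7%.
- Intervention: 1 − Φ(0) = 50.0%.
- Difference: 15.3 points. It is 12.2 at correlation 0.6 and 19.4 at 0.85.
- Standard error with 272 per arm: √[(0.347 × 0.653 + 0.5 × 0.5)/272] = 4.2 points.

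**Dependence on baseline.** Given baseline, the SD of the 12-month value is 107.9 × √(1 − 0.75²) = 71.3 m. A control 1 SD below the mean baseline is expected to gain 0.25 × 107.9 = 27.0 m and responds with probability 1 − Φ((30 − 27.0)/71.3) = 48%. A control 1 SD above responds with probability 1 − Φ((30 + 27.0)/71.3) = 21%.

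**Chance imbalance, random loss.** The standard error of the baseline difference is 107.9 × √(2/340) = 8.3 m. If the intervention arm starts 2 SE (16.5 m) higher, its mean change falls by 0.25 × 16.5 = 4.1 m.
- With the 30 m effect: Φ(−4.1/76.3) − 34.7% = 13.1 points.
- With no effect: [1 − Φ(34.1/76.3)] − 34.7% = −2.0 points.

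**Simulation.** Trials were simulated with arm, COVID (assumed 40%) and smoking (assumed 30%), neither of which affected the outcome; site was left out. There were 4,000 trials per scenario and 1,500 for each fixed imbalance. Without baseline, the risk difference was standardised over observed patients; with baseline, over all randomised patients.

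| Scenario (correlation 0.75) | As written | With baseline |
|---|---|---|
| Random loss, 30 m effect | 15.3 | 15.3 |
| Intervention arm 1 SE higher at baseline | 14.3 | 15.3 |
| Intervention arm 2 SE higher at baseline | 13.1 | 15.2 |
| 2 SE higher, no effect | −2.1 | −0.1 |
| Loss depends on baseline, intervention arm only, logit slope 0.5 per SD | 14.0 | 15.3 |
| Same, slope 1 | 12.9 | 15.3 |
| Slope 1 in both arms, retention 75% vs 85% | 14.1 | 15.3 |
| Slope 1 in both arms, equal loss | 15.3 | 15.4 |

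- **Precision under random loss.** The standard error falls by 4% (7% at correlation 0.6, 2% at 0.85). Power goes from 96% to 97% (82% to 87% at 0.6).
- **Imbalance with no effect.** Under the 2 SE imbalance, an ANCOVA standing in for the 14.5 model stays within 0.2 m of zero. The as-written −2.1 becomes −1.6 at correlation 0.85 and −2.6 at 0.6.
- **Type I error.** For intervention-only loss it is 5.9% (slope 0.5) and 8.4% (slope 1) as written, against about 5% with baseline.
- **Direction.** The table's loss cases lose low walkers preferentially. If high walkers are lost from the intervention arm instead, exact calculation gives 16.7 or 17.7 points, so the error can also favour the intervention.
- **Scoring missing patients as non-responders.** With equal 20% loss this gives 0.8 × 15.3 = 12.2 points.

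**The case against.** An unadjusted responder comparison in a randomised trial is valid. Under random loss it is unbiased, its type I error stays near 5%, and a 4% smaller standard error is a preference rather than a correction. A 2 SE imbalance arises by chance in about 5% of trials, and the shift of about 2 points is half of the 4.2-point standard error, so the ordinary confidence interval already allows for it. All of the bias comes from loss patterns that the documents do not predict. The covariate examples in section 14.3 are an open list that could include baseline, baseline outcomes will be tabulated by arm, and section 14.5 already gives a baseline-adjusted estimate for all three dichotomised outcomes.

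Most of this stands, and it limits the size of the point. It does not remove it: an open list for sensitivity analyses does not put baseline into the 14.7 model, and the adjustment needs no new data. It is also fair that the baseline term does nearly all the work. Standardising over observed rather than all randomised patients gives 15.15 against 15.21 points in the slope-1 case.

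Adding baseline weight would not repair the sign of the weight responder, which as printed counts a gain as success. That is a separate matter.

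**Conclusion.** The point holds as a recommended change. Section 14.7 omits a prognostic value that section 14.5 uses for the same outcome, and no other section supplies it. The usual cost is small: a standard error about 4% larger than necessary (2% to 7% over the assumed correlations), and a responder difference that a 2 SE chance imbalance moves by about 2 points from a true 15.3. That movement averages out over repeated trials. Bias arises only if loss depends on baseline and differs by arm, in slope or in overall rate; the stress cases move the result by 1 to 2.5 points.

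The figures rest on an assumed correlation and a Normal model. They cover 6MWT only, because the documents give no SD for weight or Borg. The primary 6MWT analysis is unaffected.

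Two smaller errors in section 14.7 also stand. The equation is printed as linear with a Normal residual, although the text calls the model logistic. SGRQ-C, a named secondary outcome in section 9.0 and Table 10, is missing from the closing list of outcomes to be analysed; generic HRQoL does not cover it, since section 11.7 assigns that to the SF-12v2.

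**What to change.** Replace the section 14.7 model with

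logit{P(y = 1)} = b0 + b1·Intervention + b2·COVID + b3·BaselineSmoker + b4·(baseline value of that outcome) + site effect,

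with no residual term, fitted to patients with an observed 12-month value. The reported quantity remains the standardised risk difference. The b4 term is the essential change. For completeness:

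- Standardise over all randomised patients. Where the 12-month visit is missing, set COVID from its scheduled date, for standardising only. The choice matters little: with assumed COVID effects of −20 m or −40 m, using all 0 or all 1 instead moved the difference by at most 0.2 or 0.5 points.
- State that patients without a 12-month value are not scored 0 in this analysis. Scoring them 0, or imputing the continuous value before dichotomising, can be shown as labelled sensitivity analyses.
- Add SGRQ-C to the list of additional secondary outcomes, analysed like the others.

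The cost is SAP wording only. Baseline values are recorded before randomisation, and the scheduled date follows from the randomisation date. The change should be made before the outcome data are analysed.

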## 5.0. ABSTRACT

Approximately 70% of patients with Chronic Obstructive Pulmonary Disease (COPD) are obese or overweight. Tobacco smoking that causes COPD also is associated with other poor health habits that can lead to obesity and cardiovascular disease. Symptoms of COPD are often non-specific and include dyspnea and exercise intolerance. COPD treatment guidelines recommend stepped escalation of inhaled medications to improve these symptoms, but make little mention of the effect of co-existing obesity or weight loss interventions because of insufficient evidence. Cardiovascular disease is a leading cause of mortality among patients with COPD, and obesity is associated with important risk factors for cardiovascular disease including dyslipidemia, hypertension, and diabetes. Comprehensive lifestyle interventions that include calorie-controlled healthy eating, increased physical activity, and behavioral self-management strategies consistently result in modest, clinically significant weight loss and associated reductions in cardiovascular risk factors. That overweight and obese patients with COPD would reap similar clinical benefits from modest weight loss is an intuitive - but untested - concept. Therefore, we are conducting a multicenter, patient-level randomized, pragmatic clinical trial to produce first-ever data on the effectiveness of an evidence-based self-directed lifestyle intervention for 12 months targeting modest weight loss and increased physical activity among overweight and obese patients with COPD. We are serving as a Protocol Leadership Group (PLG) for the National Heart, Lung, and Blood Institute's (NHLBI) "Multi-Site Clinical Trials for the Pulmonary Trials Cooperative (PTC)" in order to test if intervention participants have better outcomes through 12 months of follow-up compared to usual care control patients in terms of exercise tolerance using the *6-Minute Walk Test*. Secondary outcomes include weight loss, dyspnea using the modified Borg scale, generic and symptom-specific quality of life using the *12-Item Short Form (SF-12v2)* and *St George's Respiratory Questionnaire for COPD Patients (SGRQ-C)*, and major cardiovascular risk factors using Framingham risk score, central obesity by waist circumference, blood pressure and BMI. We will oversee enrollment of approximately 680 patients at multiple clinical sites, chosen and contracted by the PTC's Network Management Core (NEMO). As the PLG for the INSIGHT COPD trial, we will cooperate with NEMO and will provide trial oversight, and data management and reporting.

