## 11.0. MEASUREMENTS

Table 10 summarizes measurement and timing of data collection:

Table 10: Timing of measurements and data collection			
	Source	Baseline	12-month
Primary outcome			
Six-minute walk distance	Measured	x	x
Secondary outcomes			
Weight	Measured	x	x
Modified Borg Dyspnea scale	Questionnaire	x	x
12-Item Short Form (SF-12v2)	Questionnaire	x	x
St. George's Respiratory Questionnaire-C	Questionnaire	x	x
CVD risk			
Framingham Risk Score	Measured/ Calculated	x	x
Waist circumference	Measured	x	x
Blood pressure	Measured	x	x
BMI	Calculated	x	x
Other measures			
Height	Measured	x	
Leg fatigue	Questionnaire		
Spirometry	Measured	x	x
Health inventory checklist	Questionnaire	x	x
Medications	Questionnaire	x	x
Health care utilization	Questionnaire	x	x
Demographics	Questionnaire	x	
Intervention: self-monitoring; coach communications	MyFitnessPal; Keeping Track Booklets; REDCap	Throughout 12-month intervention period	

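### Does leaving the SGRQ-C out of the Section 14 outcome lists leave a secondary outcome without a planned analysis?

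*Combined protocol and SAP*

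**What the plan says.** Section 9.0 sets out to test whether intervention participants do better than usual care on a list of outcomes. The secondary part of that list includes "improvements in generic HRQoL by the SF-12v2, COPD symptom QoL by the SGRQ-C". Table 10 in Section 11.0 also files "St. George's Respiratory Questionnaire-C" under secondary outcomes, collected at baseline and 12 months, and the Abstract agrees.

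Section 14 assigns analyses by naming outcomes. Section 14.5 states that "6MWT distance (primary), weight (secondary), and post-walk modified Borg dyspnea scale (secondary) – will be modeled via mixed-effects linear regression". Section 14.7 adds responder versions of the same three: "Dichotomized secondary outcomes for 6MWT distance, weight, and post-walk modified Borg dyspnea scale will be generated". It then ends with the remaining outcomes: "Additional secondary outcomes – generic HRQoL, Framingham CVD Risk Score, waist circumference, blood pressure, and BMI – will be analyzed similarly" to those three. The SGRQ-C is in none of these sentences.

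Three more general statements bear on the point. Section 14.2 commits to hypothesis tests for the specific aims, following the descriptions in the later subsections. Section 14.3 plans covariate-adjusted sensitivity analyses that refer to the primary and secondary outcomes without exception, and says "We will report summary statistics for all baseline covariates and outcomes" by arm. Section 14.1 says "No multiplicity adjustment will be made for secondary analyses".

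**The concern.** An outcome list that drops one prespecified outcome can mean that the comparison is never run, or that it is run in a way chosen after the data are seen. The SGRQ-C is the only disease-specific quality-of-life measure in the secondary aim. The Background (Section 6.0) also uses the parent questionnaire to motivate the trial, reporting a total score 5.93 points worse in obese patients against a minimum important difference of 4 points. Section 11.7 describes four SGRQ-C scores (Symptom, Activity, Impacts, Total), and Section 14 names no score and no model. With no multiplicity adjustment for secondary analyses, an unstated choice among four scores looks like room for selective reporting.

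**Working it through.** No figure in the plan depends on this point, so the check compares lists.

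**Step 1. Secondary components in Section 9.0 against analyses named in Section 14**

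| Component | Analysis named in |
|---|---|
| Weight | 14.5 |
| Borg dyspnea | 14.5 |
| SF-12v2 (generic HRQoL) | 14.7, last sentence |
| SGRQ-C (COPD symptom QoL) | none |
| Waist circumference | 14.7, last sentence |
| Framingham score | 14.7, last sentence |
| Blood pressure | 14.7, last sentence |
| BMI | 14.7, last sentence |

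Named: 2 + 5 = 7. Missing: 8 − 7 = 1, the SGRQ-C. The count takes the SF-12v2 and blood pressure as one component each, as Section 9.0 does.

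**Step 2. Could the generic HRQoL entry cover it?** No. Sections 9.0 and 11.7 both attach that label to the SF-12v2 and give the SGRQ-C a label of its own.

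**Step 3. Is the SGRQ-C excluded?** No. Section 14 is silent on it. The between-arm test is promised in Section 9.0, and Section 14.2 says the specific aims will be tested. Because Section 14.2 points forward to lists that lack the SGRQ-C, it shows intent but does not supply a model.

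**Step 4. Is there an evident default model?** Yes. The Section 14.5 model needs a numeric outcome at time 0 and time 1. Its other terms are the arm-by-time effect, the COVID-period and baseline-smoking indicators, and random intercepts for patient and site. The SGRQ-C gives numeric scores at exactly those two visits. The five outcomes in the last sentence of Section 14.7 are sent to the same approach, and nothing about the SGRQ-C would lead an analyst elsewhere.

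**Step 5. What changes if it is analysed this way?** Coverage goes from 7 of 8 to 8 of 8. The primary test is one comparison of 6MWT distance at two-sided 0.05 and is unaffected. Secondary analyses carry no multiplicity adjustment, so no other threshold moves.

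**Step 6. How much freedom does the unnamed score leave?** If the best of four scores were picked at 0.05, the chance of at least one false positive would lie between 5% (perfectly correlated scores, assumed) and 1 − 0.95⁴ = 18.5% (independent scores, assumed). The same freedom exists for outcomes that are listed. The SF-12v2 has two component scores, which gives 5% to 1 − 0.95² = 9.75% on the same assumptions. Blood pressure is not split into systolic and diastolic. None of the five outcomes in the last sentence of Section 14.7 has a responder threshold either.

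**The case for a change.** The strongest case for a change is that a secondary comparison the protocol promises has no prespecified analysis, and that the general statements do not repair this. Section 14.2 defers to the lists. Section 14.3 promises summaries under a baseline heading and assigns no model. Where Section 14 means a list to be open, it marks the entries as examples, and the outcome lists carry no such mark. Section 14.8 calls the secondary outcomes clinically important and counts their full assessment as a reason not to stop early. Adding a list entry would cost almost nothing.

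Most of this is correct as description. The SGRQ-C is missing, and no general sentence supplies its model. What does not follow is that the comparison would go unrun or be run differently. The outcome, its visits and the between-arm test are fixed in the Aims, and only one model is on offer for numeric outcomes. The change log for version 5.10 records work on making the secondary-outcome lists agree. That suggests a missed edit rather than a decision to drop the outcome, though this is inference.

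The point about four scores stands as a general observation about how lightly Section 14.7 specifies its outcomes. It is not a defect peculiar to the SGRQ-C, and asking for a named score here but not for the SF-12v2 or blood pressure would apply an uneven standard.

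**Conclusion.** The omission is real but small: one of eight secondary components is not named in Section 14. It is a clerical gap that analysts would fill in the obvious way. No stated rule or figure gives a wrong result, and writing the entry in would record what the Aims already require without altering the primary analysis or any other listed analysis. No change to the plan follows.

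This rests on two assumptions: that the analysts read Section 9.0 together with Section 14, and that they apply the Section 14.5 model to the SGRQ-C as they do to the other numeric outcomes. If a report left the SGRQ-C out, the mismatch with the Aims and Table 10 would be plain to any reader. Section 14.1 presents secondary results as complementary to the primary finding, so the choice of SGRQ-C score cannot affect the trial's main conclusion.
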